# 9.2 Salvage regimens

Salvage regimens will be provided for trial patients who require retreatment provided adequate follow up can be maintained. All patients who are treated with a salvage regimen should be appropriately monitored for any toxicity during their treatment, this monitoring may include ECG and laboratory monitoring, and the data recorded. The STREAM central clinical team should be contacted for guidance on the appropriate monitoring in such cases. Trial patients who initiate a salvage regimen close to the end of their trial follow-up period may require treatment and follow up beyond this time point. In addition, where appropriate the Sponsor may initiate salvage regimens for patients who have completed their 132 week Study period.

The composition of the salvage regimen will be based on treatment history and DST results and be selected by the site clinicians in consultation with the central clinical team. Salvage regimens will also take into account local guidelines and availability of medicines. Patients who are unwilling or unable to be followed during their salvage regimen treatment, including those whose planned intensive phase will not be completed prior to site closure, will be referred to the National Tuberculosis Programme for management. Upon site closure, patients still undergoing salvage regimen treatment will be referred to the National Tuberculosis Programme to ensure treatment follow up and completion.

Procurement and provision of the salvage regimen for trial patients will be supported by the Sponsor as needed and site-specific approaches to ensuring availability of medicines will be developed and documented. Bedaquiline provided as IMP for the trial will be limited to 24 weeks in a salvage regimen and only utilized where trial patients initiate their salvage regimen within their 132 week Study period. Outside of the Patient's 132 week Study period, and where available, the Sponsor may, at their discretion, use bedaquiline in a salvage regimen from an alternative source. The safety and appropriateness of the salvage regimen is the responsibility of the investigator, as well as the reporting of Adverse Events.

# 9.3 Patient transfers

For patients moving out of the area, every effort should be made to continue to follow them if at all possible; this could include follow-up at another participating site.

# 9.4 Early stopping of follow-up

If patients explicitly state that they do not wish to contribute further data to the study, MRC CTU should be informed in writing of the patient's decision and a final form should be completed. Such patients who discontinue the study may not be re-randomised and will not be replaced.

# **10 DATA MANAGEMENT**

Data will be recorded on paper case report forms (CRFs) and entered into a database either at each local site or at a central location. At each visit, details of clinical findings, procedures, tests and results will be recorded in the patient's case notes and on the appropriate CRF. The CRF top copy will be sent for data entry, and the duplicate retained in the patient's Trial Folder. Entries made in the CRF must be either verifiable against source documents or have been directly entered into the CRF, in which case the entry in the CRF will be considered as the source data. Instances where data may be entered directly in a CRF will be agreed by the Sponsor and documented. The Investigator Site File and all source data should be retained until notification is given by the sponsor for destruction.

Instructions on data capture, cleaning and subsequent storage can be found in the STREAM Data Management Plan.

# 10.1 Blinding of data

The co-chief investigators will be kept masked to allocation where possible, except in instances where the knowledge is needed for the review of adverse events. However, one of the co-chief investigators, [name], will be kept entirely blinded to treatment allocation throughout the trial. The trial statisticians and data manager in the central team will not be blinded to the allocation. However, before database lock the only data summarised by treatment allocation will be within reports to the IDMC, which will not be distributed outside of the IDMC. The Trial Statisticians will be responsible for preparing the IDMC reports, and will be the only persons outside the IDMC who will have access to these reports. Should any modifications to the trial design be required, the unblinded statisticians will be excluded from the discussion.

# 11 STATISTICAL CONSIDERATIONS

# 11.1 Analysis population definitions

Only patients randomised in Stage 1 of the STREAM trial will be included in the Stage 1 analysis population.

The analysis populations for Stage 2 only include patients that are randomised after the start of Stage 2. Recruitment to Stage 2 may not begin simultaneously at all sites. Therefore, all patients randomised on or after the site-specific start date at that site will be included in the Stage 2 analysis.

## Intention-to-treat (ITT)

All randomised patients will be included in the ITT analysis population.

## Safety population

All randomised patients who have taken at least one dose of trial treatment will be included in the safety analysis population.

#### Modified intention-to-treat (mITT)

The mITT population is defined as all randomised patients that have a positive culture for *M. tuberculosis* at screening or randomisation, with the exception of patients with isolates taken before randomisation that are subsequently found to be susceptible to rifampicin, and patients with isolates taken before randomisation that are subsequently found to be resistant to both fluoroquinolones and second-line injectables (i.e. XDR-TB) on phenotypic DST. Results from the central reference laboratory will take priority over any results from local laboratories where available. Rifampicin susceptible phenotypic DST results will be confirmed by rpoB sequencing.

## Per protocol (PP)

The PP population will be the same as the mITT population with the exclusion of patients not completing a protocol-adherent course of treatment (see Section 11.2.3), other than for treatment failure, change of treatment for an adverse event or death. Treatment failure is defined as failure to attain and maintain culture negativity until the end of allocated treatment.

### 11.2 Outcome measures

Culture results obtained using acidified Ogawa (Kudoh medium) will be used in the primary analysis, although results from other culture media will be used if the Ogawa result is missing. Any culture result that is missing because the patient is no longer able to produce sputum will be treated as a negative result, providing their last 2 available culture results (from sputum samples taken at separate visits) are negative.

#### 11.2.1 Primary efficacy outcome

The primary outcome for the Stage 1 comparison between Regimen B and Regimen A is efficacy status at 132 weeks after randomisation.

The primary outcome for the Stage 2 comparison is efficacy status at 76 weeks after randomisation.

The status for all efficacy study comparisons is determined as follows:

#### **Favourable**

A patient's outcome will be classified as **favourable** if their last two sputum culture results are negative, unless they have previously been classified as unfavourable. These two sputum samples must be taken on separate visits, the latest of which being no more than six weeks earlier than Week 132 (for the Stage 1 comparison) or Week 76 (for the Stage 2 comparison), the time-points of interest for primary outcomes in the Stage 1 comparison and Stage 2 comparisons, respectively.

For the purpose of the analysis of primary outcome measures in Stage 1 and Stage 2, the visit windows for the Week 132 (for Stage 1) and Week 76 (for Stage 2) are defined as no more than six weeks prior to, or six weeks after 132 or 76 weeks, respectively, from randomisation.

The end dates in the above windows will be extended for any Stage 2 patients whose Week 76 appointment is scheduled to occur during the COVID-19 pandemic and did not occur due to restrictions on movement, unacceptable risk of exposure to COVID-19 in connection with the scheduled visit, or any other reason related to the pandemic. For those patients, the Week 76 sputum samples must be taken in a window beginning six weeks prior to the scheduled visit date and ending within the Week 84 visit window.

#### **Unfavourable**

A patient's outcome will be classified as **unfavourable** if:

- They are discontinued from their allocated study treatment and subsequently restarted on a different MDR-TB regimen.
- 2. Treatment is extended beyond the scheduled end of treatment for any reason other than making up days when no treatment was given (missed treatment) for a maximum of eight weeks. A maximum of 14 days of extra treatment (irrespective of reason) is acceptable before it is classified as treatment extension. In addition, if the intensive phase of treatment has been extended for delayed sputum conversion (maximum 8-week extension permitted) the scheduled end of treatment will also be extended by the same amount, in accordance with Section 7.3.2.
- 3. They are restarted on any MDR-TB treatment after the scheduled end of treatment, but before 132 weeks after randomisation for Stage 1 and before 76 weeks after randomisation for Stage 2.
- 4. They change their allocated study treatment for any reason other than (1) the replacement of a single drug\* or (2) for patients allocated to Regimen A when the change is as a result of changes in local guidelines and not related to any change in the patient's circumstances or condition.
- 5. Bedaquiline is started where the allocated regimen did not originally contain that drug (Regimen A or B)
- 6. A second line injectable agent is started in Regimen C.
- 7. A drug from the class of nitroimidazoles or linezolid is started.
- 8. They die at any point during treatment or follow-up.
- 9. At least one of their last two culture results, from specimens taken on separate occasions, is positive.
- 10. They do not have a culture result at Week 76 or thereafter for the Stage 1 comparison, or within the Week 76 window for the Stage 2 comparison.

11. The failure or recurrence specimen at or before the Week 76 window was a different strain to their randomisation specimen, i.e. re-infection (the Stage 2 comparison only).

Starting a single drug is not considered to be a substantial change to the regimen and therefore does not result in an unfavourable outcome, with the exception of adding bedaquiline (in Regimen A or B), a second-line injectable in Regimen C or a drug from the class of nitroimidazoles or linezolid (in any regimen).

Following publication of the revised WHO guidelines in 2018 it became more likely that a salvage regimen following bedaquiline use would contain linezolid rather than an injectable agent. To reflect the resulting imbalance in the likelihood of point 5 and 6 occurring based on drug choice, starting linezolid alone was added as an unfavourable outcome (point 7 above) in version 11.0.

For analysis of the Stage 1 comparison, re-infections with a different strain are classified as not assessable.

Only data before or within the Week 76 window will be used for the determination of the primary efficacy outcome for Stage 2, even though patient follow-up continues to end of trial. Participants with no sputum sample available at Week 76 due to Covid-19 who are not otherwise classified as unfavourable will be considered unfavourable in line with the above definition. Sensitivity analyses will reclassify these participants as i) **non-assessable** and excluded from the primary efficacy analysis, and ii) unfavourable/favourable if their culture result at their Week 68 visit is positive/negative respectively.

An extension of the intensive phase of treatment in any study arm does not constitute an unfavourable outcome, as long as the extension is in accordance with either the algorithms described in Figures 9 and 10 (section 7.3.2) for patients on Regimen B, Regimen C, or Regimen D, or the locally-used WHO 2011 long MDR-TB regimen for patients on Regimen A. Similarly, the discontinuation of drugs that are not replaced does not constitute an unfavourable outcome.

During Stage 1, a patient who has a culture result within the Week 76, but not within the Week 132 window having not otherwise been classified as unfavourable (based on the definitions above) will be regarded as **not assessable** and will be excluded from the primary analysis provided their last two cultures, from specimens taken on separate occasions, are negative; one of these cultures should be from a sample taken at week 76. Any patient who does not have a culture result within the Week 132 window and does not fulfil these criteria will be classified as **unfavourable**. These definitions apply to both Regimen A and Regimen B in Stage 1 of the trial.

### 11.2.2 Secondary efficacy outcome at Week 132 in Stage 2

Secondary efficacy analyses will be based on data from all visits occurring on or before the projected Week 96 visit of the last patient randomised i.e. approximately end of November 2021. A participant's scheduled last efficacy visit will be their latest scheduled trial visit on or before this date.

For purposes of analysis of the secondary efficacy outcome measures at Week 132 in Stage 2, a patient's outcome will be classified as **favourable** if their last two sputum culture results are

\* Excluding changes from kanamycin to amikacin

negative, unless they have previously been classified as unfavourable. These two sputum results must be from samples taken at separate visits; the latest must be no more than six weeks before their scheduled last efficacy visit.

The visit window for the scheduled last efficacy visit is defined as no more than six weeks prior to and up to six weeks after (or on 30 Nov 2021 if this is earlier) the scheduled last efficacy visit. The end dates of the window will be extended for any Stage 2 patients whose scheduled last efficacy visit was due during the COVID-19 pandemic and did not occur due to restrictions on movement, unacceptable risk of exposure to COVID-19 in connection with the scheduled visit, or any other reason related to the pandemic. For such patients, sputum samples must be taken in a window between six weeks prior to and twelve weeks after the last scheduled visit date (or on 30 Nov 2021 if this is earlier).

A patient's outcome at their scheduled last efficacy visit will be classified as unfavourable if:

- They are unfavourable at Week 76
- They start any MDR-TB treatment between their Week 76 and scheduled last efficacy visits
- They die between their Week 76 and scheduled last efficacy visits
- At least one of their last two culture results, from specimens taken on separate occasions, is positive.

A patient who does not have a culture result within the window for their scheduled last efficacy visit, having not otherwise been classified as unfavourable, will be regarded as **not assessable** and excluded from the analysis provided their last two cultures, from specimens taken on separate occasions, are negative.

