Final analysis of STREAM Stage 1, presented at the Union Conference in October 2018, found that 78.8% of participants on Regimen B, the short regimen, had a favourable outcome at 132 weeks from randomisation compared to 79.8% on Regimen A, the 20-24 month long regimen. After adjustment for the randomisation stratification factors of HIV status and centre, the difference in efficacy between the regimens was 1.0%, (95% CI -7.5 to 9.5%) meeting the pre-specified 10% non-inferiority margin. The primary safety outcome of the trial, the proportions of patients who experienced a Grade 3 or greater adverse event at any time during treatment and follow-up, was also similar on the two regimens (48.2% on the shorter regimen compared to 45.4% on the longer regimen).

Bedaquiline is a novel diarylquinoline antibiotic with bactericidal activity. In a phase II trial of patients with MDR-TB time to culture conversion was significantly less in patients receiving bedaquiline compared to those receiving an optimised background regimen only. In December 2012 the US Food and Drug Administration (FDA) approved bedaquiline as part of the treatment regimen for MDR-TB when other agents are unavailable. Stage 2 of STREAM was designed to investigate ways in which Regimen B could be improved either by removing the second-line injectable, which is associated with severe drug toxicity, or by shortening the regimen to 6 months.

In December 2018, the WHO issued revised guidelines for treatment of MDR TB following review of a meta-analysis of available trial and observational data. This included a re-classification of drugs for longer MDR-TB treatment regimens, with moxifloxacin or levofloxacin, bedaquiline and linezolid all listed in Group A (medicines that should be used in the regimen); it was also recommended that when an injectable agent is required, amikacin should be used rather than kanamycin or capreomycin.

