# 8. ASSESSMENTS AND FOLLOW-UP

## 8.1.1 Assessment schedule

See Table 5 in Section 8.1.1 for details of the assessments required for each visit for Stage 1, and Table 6 in Section 8.1.2 for details of the assessments required for each visit for Stage 2.

The intensive phase of treatment may be extended for late smear conversion or missed treatment (see sections 7.3.2 and 7.3.3). The continuation phase may also be extended for missed treatment.

For selected sites, at randomisation and every 12 weeks thereafter, patients will be interviewed to document the costs e.g. transport and hospitalisation costs, incurred by them in adhering to the regimen. System costs will also be estimated.

#### Stage 1

In Stage 1, patients will be assessed at screening, randomisation (Week 0), Week 1, Week 2, Week 3, Week 4, and at 4-weekly intervals throughout the study, until the end of follow-up, irrespective of whether on treatment or in the post-treatment follow-up phase.

Sputum for smear and culture will be collected at every visit, except at Week 1, Week 2, and Week 3, when no samples will be collected. At most visits this will be a single specimen during Stage 1, unless otherwise indicated in section 8.1.1. When two samples are required, if a patient does not bring an early morning sample, two spot samples will be collected at the visit.

### Stage 2

In Stage 2, patients will be assessed at screening, randomisation (Week 0), Week 1, Week 2, Week 3, Week 4, after which they will be seen 4-weekly until Week 52, then 8-weekly until Week 84, and 12-weekly thereafter until end of trial follow-up.

A minimum of two sputum specimens should be collected at the screening and randomisation visit (with a third being an early morning sample if possible).

Two sputum specimens will be collected at every subsequent visit for smear and culture, except at Week 1, Week 2, and Week 3, when no samples will be collected. Because early morning samples are preferred, at the conclusion of each visit patients should be given a sputum container for sample collection to be presented at their next visit. The second sample will be taken as a spot sample at the time of clinic attendance. If a patient does not bring an early morning sample, two spot samples will be collected at the visit.

Routine sputum collection will end when the last patient is projected to have reached Week 96 (approximately end of November 2021). Thereafter sputum will be collected only if clinically indicated.

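### The Stage 1 not-assessable rule is tied to the Week 76 sample, so a culture-negative patient last sampled at Week 120 is scored unfavourable while one lost just after Week 76 is excluded

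*Protocol*

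**What the plan says.** In Protocol section 11.2.1 the Stage 1 rule for a missing Week 132 culture applies to "a patient who has a culture result within the Week 76, but not within the Week 132 window having not otherwise been classified as unfavourable". Such a patient is not assessable, and leaves the primary analysis, "provided their last two cultures, from specimens taken on separate occasions, are negative". A further condition follows: "one of these cultures should be from a sample taken at week 76". The next sentence sets the default: "Any patient who does not have a culture result within the Week 132 window and does not fulfil these criteria will be classified as" unfavourable.

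Three other places bear on this rule:

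- Section 8.1.1 schedules Stage 1 visits "at 4-weekly intervals throughout the study, until the end of follow-up", with sputum for culture at each visit after Week 3. Section 11.2.1 sets the Week 132 and Week 76 windows at six weeks either side, so Weeks 126 to 138 and Weeks 70 to 82.
- Item 10 of the unfavourable list in 11.2.1 reads "They do not have a culture result at Week 76 or thereafter for the Stage 1 comparison".
- Section 11.2.2, the Stage 2 rule for Week 132, makes a patient with no culture in the final window not assessable and "excluded from the analysis provided their last two cultures, from specimens taken on separate occasions, are negative". It does not ask that either of those two cultures be the Week 76 sample. SAP section 7.1.4 has the same form and adds that all remaining patients are unfavourable.

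**The concern.** A rule for incomplete follow-up should not treat a patient worse for having supplied more evidence of cure. This one does. A patient who stays culture negative well beyond Week 76 and then misses the Week 132 window has last two cultures that no longer include Week 76. That patient falls into the default and counts as a failure, while a patient who disappears right after Week 76 is dropped.

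The rule operates on the Stage 1 primary endpoint. Losses over the affected weeks need not balance between arms: section 11.3.1 puts Regimen A at 104 weeks and Regimen B at 40, so for part of the interval one arm is still on treatment and the other is not. Section 2.1.1 reports the Stage 1 difference with "95% CI -7.5 to 9.5%) meeting the pre-specified 10% non-inferiority margin", so the upper limit lies 0.5 point inside the margin. A reader should be able to tell from the protocol how each patient behind that figure was classified.

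**Working it through.** **Classification.** Take a patient with four-weekly cultures, all negative, and no other unfavourable event. Let L be the week of the last culture, so the last two cultures are at L - 4 and L.

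| Last culture, L | Literal rule, sample at Week 76 itself | Literal rule, any sample in Weeks 70-82 | Rule as proposed under the fix |
|---|---|---|---|
| 76, 80 | not assessable | not assessable | not assessable |
| 84 | unfavourable | not assessable | not assessable |
| 88 to 124 | unfavourable | unfavourable | not assessable |
| 128, 132 | favourable | favourable | favourable |

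There are 13 scheduled visits from Week 76 to Week 124. On the strict reading, 11 of them (Weeks 84 to 124) give unfavourable if they are the last culture. On the window reading, 10 do (Weeks 88 to 124). With L = 120 the last two cultures are at Weeks 116 and 120, and the patient fails on either reading. With L = 76 they are at Weeks 72 and 76, and the patient is excluded.

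**Reported figure.** Sections 2.1.1 and 2.2 give favourable rates of 79.8% on A and 78.8% on B. The difference is 79.8 - 78.8 = 1.0 point, as stated. The interval -7.5 to 9.5 is centred at 1.0 with half-width 8.5.

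**Effect of correcting the literal rule, if that rule was used.** Correction moves k patients from unfavourable to excluded, so an arm's rate changes from p to p × n/(n - k). Assumptions: planned sizes nA = 133 and nB = 267, unadjusted rates, constant half-width.

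- One unmatched B patient: 78.8 × 267/266 = 79.1, so A minus B moves by -0.30.
- Two unmatched B patients: 78.8 × 267/265 = 79.4, a move of -0.59; the upper limit would be about 8.9.
- One unmatched A patient: 79.8 × 133/132 = 80.4, a move of +0.60; the upper limit would be about 10.1.
- Proportional losses, 3 on A and 6 on B: A rises by 79.8 × 3/130 = 1.84 and B by 78.8 × 6/261 = 1.81, a net move of +0.03.

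With 120 and 240 analysed instead, the per-patient moves are 78.8/239 = 0.33 for B (downward) and 79.8/119 = 0.67 for A (upward).

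**Illustration at the design rates.** Suppose a fraction x of an arm is lost culture negative, spread evenly over the 13 visits, and the rest are favourable at the planned 70% (A) or 75% (B). The strict rule excludes 2/13 of the lost patients, so the observed rate is (1 - x)p / (1 - 2x/13). The corrected rule returns p, and A minus B is -5.0.

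- x = 5% in both arms: 67.0 - 71.8 = -4.8.
- x = 10% on A and 5% on B: 64.0 - 71.8 = -7.8.
- x = 5% on A and 10% on B: 67.0 - 68.6 = -1.5 (from unrounded rates).

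Equal loss barely moves the difference. Unequal loss moves it in either direction. The loss fractions are assumptions; the documents give none.

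**The case against.** The best defence is that this is loose drafting with a plain intent. Item 10 speaks of Week 76 or thereafter, and an analyst may well have programmed that. A separate Stage 1 SAP exists (SAP, General Information), covers all Stage 1 analyses, and may define the category properly. The affected group is also narrowed: section 11.2 treats a culture as negative when the patient can no longer produce sputum after two negatives, and section 8.5.5 seeks a final sample from patients who decline further participation. All of this stands and limits the likely impact. It does not repair the text, since no supplied section overrides the default sentence. The softer verb in the Week 76 condition does not help either, because failing the criteria leads to unfavourable.

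Two stronger readings are tempting and go too far:

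- A reader might infer that the rule formally contradicts item 10. Item 10 names one sufficient reason for an unfavourable outcome and does not say it is the only one for a missing culture. The two fit poorly, but the not-assessable rule can be read as adding a further default.
- A reader might infer that Stage 2 has no Week 76 requirement at Week 132. It does, indirectly: section 11.2.2 carries forward anyone unfavourable at Week 76, and item 10 makes a Stage 2 patient with no Week 76-window culture unfavourable. What Stage 2 lacks is the demand that one of the last two cultures be the Week 76 sample.

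**Conclusion.** The rule is wrong as written. It reverses the sensible ordering for culture-negative patients whose last culture falls at Weeks 84 to 124 (Weeks 88 to 124 on the window reading), and it does so in the Stage 1 primary endpoint.

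Its effect on the reported result cannot be determined. The documents do not say how many patients were affected in either arm or which rule was programmed. If the sensible rule was used, the result stands and only the text needs changing. If the literal rule was used, correction moves A minus B by about -0.3 point per unmatched B patient and +0.6 per unmatched A patient, and by about zero with proportional losses, under the planned sizes, unadjusted rates and constant interval width assumed above.

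Because the limit is 0.5 point inside the margin, a reader might infer that the Stage 1 conclusion fails or is close to failing. The documents do not support that. An excess of affected B patients would strengthen non-inferiority on correction. Only an excess on A would weaken it, and no counts are given. The reported interval was also adjusted for HIV status and centre, which this arithmetic is not. Nor does Regimen B's role as Stage 2 control rest simply on this result: section 2.2 says Stage 2 began without randomised evidence that B was non-inferior to A. The Stage 2 primary outcome is untouched.

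**What to change.** In section 11.2.1, delete the clause "one of these cultures should be from a sample taken at week 76". Change the entry condition of the same sentence so that it admits a patient with a culture in the Week 76 window or at any later time, but none in the Week 132 window. Keep the requirement that the last two cultures, from separate occasions, are negative. Both edits are needed. Without the second, a patient who misses the Week 76 window but is negative at later visits satisfies item 10 and still falls into the unfavourable default.

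State which rule produced the reported Stage 1 analysis. If it was the literal one, give the reclassified estimate and interval beside the reported ones, in both the mITT and per-protocol populations, with the number reclassified in each arm.

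The cost is one sentence of protocol text and a check, or one re-run, of an existing classification program. As Stage 1 has been reported, the practical downside is that a clarification may need to be published.
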